# 5 Trial design

The initial phase will involve the adaptation of the intervention and development of the CST manual for people with Learning disabilities and dementia, as well as the development of the CSRI resource use questionnaire.

1. Recruitment of Participants in accordance with the inclusion and exclusion criteria & Baseline assessments

Participants will be recruited and selected in accordance with the inclusion and exclusion criteria. They will then be assessed prior to the groups with the outcome measures selected.

2. Training of professionals in CST delivery

Professionals in the participating trusts will be trained in the delivery of CST groups which will be provided by the research team. Support around reasonable adjustments to the materials in order for them to be delivered to the ability level of the participants would also be provided to potential group facilitators.

#### 3. Feasibility Randomised Controlled Trial

This will be a single blind, pilot randomised controlled trial of CST delivered by professionals versus treatment as usual. Fifty participants will be randomised to either the intervention group or control group (treatment as usual). Randomisation will occur after baseline assessments are completed. Each arm will have 25 participants and they will be allocated to one CST group with up to five participants in each group.

The duration of the intervention will be 7 weeks. There will be assessments at baseline during the two weeks prior to randomisation, and at the end of the intervention after 8-9 weeks.

Please refer to figure 1 which shows the overall trial design.

#### Figure 1: Trial schematic diagram

## 6 Selection of Participants

#### 6.1 Inclusion criteria

- 1. Premorbid mild or moderate Learning disabilities (based on clinical notes)
- 2. ICD-10 diagnosis of mild or moderate dementia
- 3. Is able to provide informed consent or where the participant lacks capacity, he/she has a personal consultee who has agreed to the participant taking part in the study.
- 4. To be able to communicate in English

#### 6.2 Exclusion criteria

- 1. Severe Learning disabilities, preventing engagement in CST groups
- 2. Severe or late stage dementia
- 3. Has a visual impairment or hearing impairment that may interfere with the participant taking part
- 4. Has significant physical illness or disability preventing their participation
- 5. Has significant behavioural problems that could affect participation (e.g. aggressive behaviour)

Participants receiving anticholinesterase inhibitors as part of their usual treatment will not be excluded.

#### 6.3 Recruitment

Participants will be recruited from community learning (Learning) disability teams based within the participating 5 NHS trusts including North East Foundation trust (NELFT), Central North West London Foundation Trust (CNWL), Camden and Islington (C&I), Barnet, Enfield and Haringey (BEH) and East London foundation trust (ELFT). The recruitment will be through the Learning Disabilities Teams in the first instance they will contact possible participants and gain consent to be contacted by the research team. The participants will likely be from multiple types of settings, including people who live in supported living, residential and family homes.

The Paticipants will have been diagnosed (or will be strongly suspected of having dementia) by a clinical psychologist and/or psychiatrist. Psychiatrists/psychologists will be asked to screen their case load for possible participants. Participants will then be approached by members of the multidisciplinary team who work closely with the participant and will discuss the study with the participant and their carer. If they are interested in taking part, they will be provided with an information sheet and their details will be passed on to the trial research assistant or CI. The research assistant will then contact the participant and their carer by phone and will arrange a meeting to

answer questions and to assess eligibility. If the participant (or a consulting carer) agree to taking part then informed consent will be obtained from the participant or consulting carer.

Participant recruitment at a site will only commence when the trial has:

- 1. Been confirmed by the Sponsor (or its delegated representative), and
- 2. Has received REC Favourable opinion and HRA Approval

#### 6.4 Informed consent

It will be the responsibility of the research team to obtain written informed consent from each participant prior to participation in the trial, following adequate explanation of the aims, methods, anticipated benefits and potential hazards of the trial.

The person taking consent will be suitably qualified and experienced, and will have been delegated this duty by the PI of each of the sites on the Staff Signature and Delegation of Tasks.

"Adequate time" will be given for consideration by the participant before taking part. Consent will be sought at least 24 hours after being given the study documentation and obtained with a carer present. It must be recorded in the medical notes when the participant information sheet (PIS) has been given to the participant.

The Investigator or designee will explain that participants are under no obligation to enter the trial and that they can withdraw at any time during the trial, without having to give a reason.

No trial procedures will be conducted prior to the participant giving consent by signing the consent form. Consent will not denote enrolment into trial.

A copy of the signed Informed Consent form will be given to the participant. The original signed form will be retained in the trial file at site and a copy placed in the medical notes.

Where the participant loses capacity within the trial the PIS and consent form will be reviewed and updated if necessary throughout the trial (e.g. where new safety information becomes available) and participants will be re-consented as appropriate. If the participant is found to have lost capacity a personal consultee will be requested to provide a declaration. Where there is no personal consultee a nominated consultee will be requested.

#### Participants lacking capacity

The intervention will be taking place with participants who are able to provide informed consent at the time of consenting. However this might change through the duration of the study and therefore consent will be sought throughout the study period.

Capacity to take part in the research will be assessed by the delegated professional who will receive training on assessing capacity. He/she will determine whether the participant broadly understands the nature and purpose of the research and the risks and benefits of taking part or not taking part; whether the participant is able to retain the information; whether they can weigh up the pros and

cons of taking part in the research and whether they can communicate the decision (verbally or non verbally).

Where the participant found to be lacking capacity, we will follow the guidelines stipulated in the Mental Capacity Act (2005) in relation to including participants lacking capacity in research. A personal consultee will be consulted to consider the participant's beliefs and wishes about taking part in the study and will need to sign the declaration form before the participant is included in the study. If a personal consultee is not available, then we will consider approaching a nominated consultee (a member of the clinical team not directly involved in the research) to provide written agreement.

# 7 Product/Interventions

## 7.1 Name and description of intervention(s) under investigation

#### Group CST intervention

The intervention will comprise of 14 face to face sessions of CST based on a treatment manual. Each session will begin with discussion of the day, date, weather and location (5 mins) followed by discussion of events in the news or current issues (10 mins) and then the main activity (30 mins). The activities are based around a themed activity (e.g. life story, discussion of current affairs, being creative), which are designed to be mentally stimulating.

Two designated professionals from the Learning Disabilities team will be the group facilitators over a period of 7 weeks, 2 times per week. The groups will be run by professionals in the health team only, carers will not facilitate groups at any point. The activities will be tailored to the abilities and interests of the individuals with ID. Group facilitators will be asked to fill in the group monitoring sheet provided at the back of the CST manual. They will also receive advice and tips on how to adjust parts of the group programme to the level of ability of participants with ID and dementia i.e. using visual cues and replacing words with pictures where possible.

The intervention group will continue to have access to their usual care, which includes input from health and social care professionals, anti-dementia medication and their usual day activities.

#### Control group

The control group will have access to their usual care only for the duration of the trial. At the end of their participation in the study, once follow up data has been collected, the professionals can offer the groups to those who were in the control arm of the study. They will also continue to have access to support and care from their community learning disability service. To avoid disparity in care we will ensure that only one person per residential or supported living home is recruited. We will inform the participants that they may not receive the intervention if they are in the control group.

## 7.2 Storage and handling of drug at site (if applicable)

Not applicable

## 7.3 Accountability of drug (if applicable)

Not applicable

## 7.4 Concomitant medication (if applicable)

The participants will be permitted to take any medication that they usually take, including medication that may enhance cognition (e.g. acetyl cholinesterase inhibitors). These will be recorded carefully at baseline and follow up.

Concomitant medications will be recorded in the participant's medical records and in the trial's CRF.

## 7.5 Dosages, modifications and method of administration (if applicable)

Not applicable as the research team will not be administering any drugs.

## 8 Trial procedures

#### 8.1 **Pre-intervention assessments**

All the participants with dementia and Learning disability will be screened for the presence of dementia based on ICD-10 criteria by the research team. This will be assessed using the criteria from the CAMDEX-DS. If the participants meet the criteria, they will complete the following baseline assessments (at home) prior to randomisation we will also collect demographic information of the participant. This will be done face to face with the carer present and following the outcome measures guideline instructions. The researcher will take with the hard copies of the assessments and enter data in the online system within 48 hours.

The outcome measures will be completed before the randomisation process and during week 8 and 9, after the intervention. The outcome measures have been described in the table below:

Type of	Name of measure	Comments	Rated by
measure			
Cognition	Severe Impairment Battery (SIB)	Originally developed for people with severe dementia in the general population, it has been used to assess dementia in people	Administered by researcher to individual with dementia (Direct assessment)

		with ID. Takes approx. 20 mins to complete.	
		Assess 6 subscales: orientation, attention, language, memory, visuo-spatial ability, construction.	
		Evidence suggests that it has good test-retest and concurrent validity in people with ID.	
Cognition	Dementia Questionnaire for people with Learning Disabilities (DLD)	Widely used in clinical practice and for measuring change in symptoms over time. Eight subscales split into two categories: Cognitive Score and Social Score Reference:	Completed by carer
Quality of Life	Quality of Life in Alzheimer's Disease (QOL- AD)- Proxy version	13 item scale covering physical health, mood, family life and functioning. Not developed for use in ID population but was used in iCST study and found to have a large effect size	by carers
Symptoms of depression	Glasgow Depression Scale for People with Learning Disability (GDS- LD) proxy version	16 item scale. Good internal consistency and inter-rater reliability.	Rated by carer
Health related Quality of Life	EQ-5D-5L	The EQ-5D-5L is a 5-item health utility instrument that captures participants' self-rated status in five dimensions: mobility, self-care, usual activities, pain/discomfort and anxiety/depression; according to five levels: no problems, slight problems, moderate problems, severe problems and extreme problems. There is also an accompanying visual analogue scale (0-100) that is completed at the same time for valid use of the questionnaire. The responses to the five dimensions are	Rated by individual

		transformed into a single utility	
		score using an algorithm, and the	
		utility score is scaled with	
		1=perfect health and 0 being	
		equivalent to dead. The utility	
		score can be used to calculate	
		quality-adjusted life-years, if the	
		EQ-5D-5L is captured across more	
		than one timepoint.	
Health related	EQ-5D-5L- Proxy	This is the same questionnaire as	Rated by carer (carer
Quality of life	version 1	above, and the carers will be asked	reports person's QoL based
		to complete it by proxy for the	on their own opinion)
		dementia patient.	
Health Service	Client Services	This questionnaire captures	Completed by carer
Utilisation	Receipt Inventory	information on health and social	
	(modified	care resource use, such as primary	
	version)	and community health care,	
		medications, routine and	
		emergency hospital care and use of	
		personal social services, provided	
		either by the state or funded	
		privately, as well as financial or	
		related impacts on carers. Costs	
		will be calculated by applying	
		standard unit costs to the	
		information gathered via the CSRI.	

All pre-treatment procedures will be carried out as specified in the schedule of assessments.

## 8.2 Randomisation Procedures

Randomisation will occur after eligibility, consent and baseline assessments have been carried out by the blinded research assistant. Randomisation will be undertaken by the coordinating trials unit (NWORTH) using a dynamic adaptive randomisation algorithm via a secure online interface. An unblinded member of the team will enter necessary details into the web based randomisation system. This system will randomly allocate the participant to either the intervention or control arm. Randomisation will be stratified for recruited NHS Trust site/centre. Participants will be randomly allocated to intervention group or control group and informed of group allocation by an unblinded member of the research team. Although participants cannot be blinded to their allocated group, the research assistant administering the questionnaires will be blinded to the allocation group. Due to the risk of carers revealing the allocation group, participants and their carers will be reminded before the follow-up assessments not to divulge this information. At the end of the study, we will assess researcher blindness by asking them to guess the allocated group.

#### 8.3 Intervention procedures

Group Cognitive Stimulation Therapy is a group intervention for people with mild to moderate dementia designed following extensive evaluation of the available research and is an evidence-based treatment. The programme consists of fourteen 45-minute sessions which are run twice weekly over 7 weeks. Each session incorporates use of a reality orientation board, displaying both personal and orientation information, including the group name (as chosen by participants). The guiding principles of CST involve using new ideas, thoughts and associations; using orientation (but sensitively and implicitly); a focus on opinions rather than facts; using reminiscence as an aid to the here-and now; providing triggers to aid recall; creation of continuity and consistency between sessions; focus on implicit (rather than explicit) learning; stimulating language; stimulating executive functioning and being person-centred - (treating people as unique individuals with their own personality and preferences). The CST programme aims to create an environment where people have fun, learn and where they strengthen their abilities and relationships among the group members, thus maintaining their social and cognitive skills at their optimum ability.

As part of a NELFT service evaluation, CST was delivered to a group of patients with comorbid ID and dementia including a reduced number of group participants with a maximum of five people in each group. The activities within sessions used visual aids to convey information about time and place, "easy read" newspaper articles to discuss current events, and simplified activities within each theme so that they were accessible to people with ID. Within the original structure of CST, sessions are allowed to be flexible in order for the activities to be adapted to different interests as well as different levels of cognitive function.

## 8.5 Samples (if applicable)

Not applicable

## 8.6 Discontinuation/withdrawal of participants

A participant may be withdrawn from trial whenever continued participation is no longer in the participant's best interests, but the reasons for doing so should be recorded. Reasons for discontinuing the trial may include:

- disease progression whilst in trial
- Chronic current illness
- patients withdrawing consent or Personal/Nominated Consultees withdrawing assent for participants lacking capacity

The decision of a participant to withdraw from treatment will be recorded in the CRF and medical notes. If a participant withdraws from the intervention, they will be asked to continue to provide follow up data. Their decisions regarding withdrawal from the intervention and withdrawal from follow-up will be recorded in their medical notes and in the trial CRF, along with any reasons that they have shared.

## 8.7 Definition of End of Trial

The expected duration of the trial is 30 months from recruitment of the first participant.

# 8 Recording and reporting of adverse events

## 9.1 Definitions

Term	Definition
Adverse Event (AE)	Any untoward medical occurrence in a patient or trial participant, which does not necessarily have a causal relationship with the intervention involved.
Serious Adverse Event (SAE).	
 
Any adverse event that:
 
results in death,
 
is life-threatening*,
 
requires hospitalisation or prolongation of existing hospitalisation**,
 
results in persistent or significant disability or incapacity, or
 
consists of a congenital anomaly or birth defect.
 

* A life- threatening event, this refers to an event in which the participant was at risk of death	

\* A life- threatening event, this refers to an event in which the participant was at risk of death at the time of the event; it does not refer to an event which hypothetically might have caused death if it were more severe.

\*\* Hospitalisation is defined as an in-patient admission, regardless of length of stay. Hospitalisation for pre-existing conditions, including elective procedures do not constitute an SAE.

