# 9.2.3 Expectedness

Category Definition	
---------------------	--

Expected	An adverse event which is consistent with the information about the intervention listed in the SPC, manual of Operation (amend as appropriate) or clearly defined in this protocol.
Unexpected	An adverse event which is not consistent with the information about the intervention listed in the SPC, manual of Operation (amend as appropriate)* or clearly defined in this protocol.

\* This includes listed events that are more frequently reported or more severe than previously reported.

There are no known adverse effects of Cognitive Stimulation Therapy. However, taking part may possibly cause distress/ inconvenience for some participants with dementia

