# **14** Oversight Committees

## **13.1** Trial Management Group (TMG)

The TMG will include the Chief Investigator and trial staff. The TMG will be responsible for overseeing the trial. The group will meet regularly (four times a year) and will send updates to Trust PIs.

The TMG will review recruitment figures, SAEs and substantial amendments to the protocol prior to submission to the REC. All PIs will be kept informed of substantial amendments through their nominated responsible individuals.

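### The SAE footnote in 9.1 leaves unplanned admissions for worsening dementia or learning disability outside the hospitalisation criterion

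*Protocol*

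**What the plan says.** Protocol 9.1 lists as one SAE criterion an event that "requires hospitalisation or prolongation of existing hospitalisation". The footnote to that criterion is broad at first: "Hospitalisation is defined as an in-patient admission, regardless of length of stay". Its next sentence then takes a class of admissions out: "Hospitalisation for pre-existing conditions, including elective procedures do not constitute an SAE".

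Under 6.1, every participant must have a premorbid mild or moderate learning disability and an "ICD-10 diagnosis of mild or moderate dementia". Section 8.6 names progression of the disease as a possible reason for leaving the trial.

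On harms, 9.2.3 states that CST has no known adverse effects but that "taking part may possibly cause distress/ inconvenience for some participants with dementia". Section 9.2.2 singles out events related to CST as ones the trial particularly needs to capture.

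The reporting routes are in 9.3 and 9.4. All adverse events go in the CRF. SAEs also go on the sponsor's log and on a form sent to the sponsor, preferably within 5 working days. Unexpected events thought to be related go to the Health Research Authority within 15 days. On oversight, 13.1 says: "The TMG will review recruitment figures, SAEs and substantial amendments to the protocol".

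**The concern.** In the footnote, elective procedures are one case within a wider class, and the class is every hospitalisation for a pre-existing condition. Such a carve-out is harmless when it covers planned admissions for a stable condition. Here it also covers unplanned admissions for a condition that has got worse, and the condition under study is itself pre-existing in everyone enrolled.

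What is at stake is the speed and level at which such an admission is looked at. If participation contributed to a deterioration that led to admission, the event could be classed by its reason for admission and so never enter the SAE procedure, whatever causality was later assigned to it.

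**Working it through.** No arithmetic applies, because the point turns on wording. The check traces one event through the protocol: a participant has an unplanned in-patient admission because their dementia has deteriorated.

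1. **Is it a hospitalisation?** Yes. Under 9.1 any in-patient admission counts, whatever its length.
2. **Is the condition pre-existing?** Yes. Dementia and learning disability are both entry requirements in 6.1, so this holds for all 50 planned participants.
3. **Does the footnote remove it?** Yes. The footnote does not separate planned from unplanned admissions, or stable from worsened conditions.
4. **Does any other text restore it?** No. Nothing in 9.1 to 9.5 brings admissions for worsening back. Section 9.2.2 refers to a section 9.17 for reporting requirements, but the adverse event section ends at 9.10, so no separate route for CST-related events is shown.
5. **Can another SAE criterion apply?** Yes, in some cases. The footnote marker is on the hospitalisation criterion alone. Death, threat to life, and lasting or marked disability remain separate criteria. An admission for deterioration that meets none of these is the case left open.

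For that remaining case, the routes compare as follows:

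| Route | If the admission is an SAE | If the footnote removes it |
|---|---|---|
| CRF entry (9.3) with severity, causality, seriousness and expectedness (9.2) | Yes | Yes |
| SAE form to sponsor, 5 working days (9.4) | Yes | No |
| Sponsor's log of SAEs (9.4) | Yes | No |
| Health Research Authority, 15 days (9.4) | If related and unexpected | No: it falls outside the SAE procedure |
| TMG review of SAEs (13.1) | Yes | Not provided for |

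The event is therefore recorded, but it misses the expedited routes and the stated SAE review. The exclusion also acts before causality matters: reason for admission decides SAE status, so a judgement under 9.2.2 that the event was probably related to CST would not bring it back.

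**The case against.** The strongest reply is that little is lost. The event is still in the CRF with a causality judgement. The modified CSRI asks carers about routine and emergency hospital care. Section 9.10 sends incidents that meet its definition to the Trust through DATIX. The sponsor SOPs cited in 9.2, and the study-specific SAE procedure mentioned under Monitoring, are not shown and may deal with worsening. The authors may have meant planned admissions only. CST is a non-invasive 7-week programme, and 3.1 already says what to do if a session causes distress. The Health Research Authority route would in any case concern only events judged both related and unexpected.

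Much of this stands, and it limits severity. It does not close the gap. None of these other routes is stated to produce an SAE form or to reach the TMG, and a site will apply the definition as printed.

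Four stronger readings are tempting, and the protocol does not support them:

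- **That 9.1 contradicts 9.5.** Section 9.5 says that no category of SAE is exempt from reporting. Section 9.1 decides what is an SAE at all. An event outside the definition is not an exempted SAE, so both statements can hold.
- **That the TMG sees SAEs and nothing else.** Section 13.1 names SAEs among the items reviewed and gives the TMG general oversight. It does not restrict the TMG to SAEs. What can be said is that no review of other adverse events is stated.
- **That behavioural admissions are equally excluded.** Section 6.2 keeps out people whose significant behavioural problems could affect participation. A new behavioural crisis is not plainly a pre-existing condition, and it would be removed only if attributed to the dementia or learning disability.
- **That the SAE count passed to the definitive trial will be too low.** No objective or progression criterion in section 4 uses an SAE count.

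**Conclusion.** The point holds as a defect in a stated rule. By its wording, the footnote in 9.1 keeps unplanned admissions for deterioration of dementia or learning disability out of the hospitalisation criterion, and hence out of SAE handling unless another criterion is met. It can apply to any of the 50 participants. How often it would apply cannot be said: the protocol gives no admission rate, and none is assumed here.

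The conclusion rests on two assumptions: that sites follow the protocol's text, and that the SOPs not shown do not qualify it. Severity is low to moderate. The intervention is low risk and the event is not lost from the record, but the gap covers the whole trial population and weakens the capture of CST-related events that 9.2.2 asks for.

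**What to change.** Rewrite the footnote sentence in 9.1 so that it excludes only planned or elective admissions, arranged before consent, for a pre-existing condition that has not worsened. Add that unplanned admissions, and admissions for worsening of a pre-existing condition, count as SAEs and follow 9.4 in both arms. In 9.2.2, correct the reference to section 9.17 so that it leads to the reporting section that applies. If a sponsor SOP already contains the narrower rule, carry it into 9.1 rather than leave the two to differ.

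The cost is a sentence or two in 9.1 and one corrected cross-reference, submitted through the amendment route in the ethics section, plus some extra SAE forms. With 50 participants followed for about 8 to 9 weeks, a few is a reasonable expectation, but that is a judgement and not a figure from the protocol. Some of the extra forms will describe ordinary progression of dementia, and the causality and expectedness assessments already in 9.2 can sort these.
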